5.2. Subject Dispositions

All disposition summaries will be in a n (%) format, i.e. a frequency count with accompanying percentage.

5.2.1. Definition of disposition variables

For all disposition variable definitions for the core study (such as subjects randomized, subjects treated, subjects discontinued treatment/study, etc.), refer to the core study SAP. These variables will be used as derived in the core.

5.2.1.1. Enrolled subjects in the extension study

Subjects enrolled are those subjects who have signed the Informed Consent Form for the extension study (per the 'Informed Consent' eCRF module).

5.2.1.2. Treated subjects in the extension study

A subject is considered treated if they received at least one dose of ponesimod in the extension study and signed the informed consent form for the extension study.

5.2.1.3. Subjects completing the core treatment and study as per protocol and not entering the extension

A subject is considered to meet these criteria if they completed treatment and study in the core per protocol (according to the corresponding definition included in the core study SAP) and did not subsequently enter the extension study.

5.2.1.4. Subjects prematurely discontinued from treatment in the extension

See definition in Section 5.4.1.1.

5.2.1.5. Subjects completed study in the extension as per protocol

See definition in Section 5.4.1.1.

5.2.1.6. Subjects prematurely discontinued from study in the extension

A subject is considered to have prematurely discontinued from study in the extension if a reason for study stopped and a date of discontinuation ('Date of last successful contact') is reported in the eCRF page "Study Discontinuation". See also Section 5.4.1.1.8 for more details.

5.2.1.7. Subjects prematurely discontinued from treatment or study in the extension

Subjects are considered to have prematurely discontinued from treatment or study in the extension if they prematurely discontinued from treatment in the extension, or they prematurely discontinued from study in the extension, or both.

5.2.1.8. Subjects interrupted treatment for planned pregnancy in the extension

Subjects who interrupted treatment for planned pregnancy in the extension have a record in the extension eCRF labeled 'Maintenance Ponesimod' form with reason for treatment end given as 'Temporarily interrupted due to planned pregnancy as defined in the protocol' and without first study drug intake date in the extension eCRF 'Study drug administration- Re-initiation after planned Pregnancy' form. The duration of treatment interruption due to planned pregnancy is defined as [min (EOS date, end date of pregnancy interruption) – Start date of pregnancy interruption + 1]. Duration of treatment interruption due to planned pregnancy is excluded from all definitions of exposure durations and compliance with study treatment.

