1. INTRODUCTION

This statistical analysis plan (SAP) contains definitions of analysis populations, derived variables, and statistical methods for the analysis of efficacy and safety for the extension study 67896153AC-058B303, following the unblinding of the core study AC-058B301 (OPTIMUM), as planned in the AC-058B303 protocol.

The SAP consists of selected efficacy and safety analyses. Data from the extension study are pooled with that of the corresponding core study AC 058B301 (OPTIMUM). Statistical analysis will be descriptive unless otherwise stated. A database lock for final analysis will occur after all enrolled subjects in the extension study have completed the end of study visit or prematurely discontinue the study.

This document is based on the AC-058B303 protocol Final Version 6, dated 15 March 2022, and Version 6.UKR.A dated 04 August 2022.

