5.1.6. Definition of treatment-emergent

A safety assessment (ECG, vital signs, laboratory, etc.) is considered treatment-emergent relative to the Analysis Period, and a safety event (AE, serious adverse event [SAE], Death, etc.) is considered treatment-emergent relative to the Analysis Period, if the assessment date is on or after the study treatment start date in the Analysis Period and prior to or on the study treatment end date + 15 days (inclusive). In case of planned pregnancy interruption, a safety assessment is considered treatment emergent relative to the Analysis Period if one of the following conditions is met:

- the assessment date is on or after the study treatment start date in the Analysis Period and prior to or on the last study drug intake date prior to pregnancy interruption + 15 days (inclusive)
- the assessment date is on or after the re-initiation date of study treatment after planned pregnancy and prior to or on the End of Treatment (EOT) date + 15 days (inclusive).

In case of multiple planned pregnancies interruptions, the above definition will be adapted, that any assessment in the following interval is not considered as treatment emergent: date between the last study drug intake date prior to each pregnancy interruption + 15 days (inclusive) and the reinitiation date of study treatment after each planned pregnancy (excluded).

If both the assessment date/time and the date/time of study treatment start (or of re initiation after planned pregnancy) are available, only events with date/time on or after the date/time of study treatment start (or of re initiation after planned pregnancy) are considered to be treatment emergent. In case of (partially) missing assessment dates/times, or for assessments on treatment Day 1 with reported assessment time contradicting the time point label, the nominal visit and time point labels will be used to determine whether an assessment is considered as treatment-emergent or not. For example, a blood pressure measurement with an assessment date on Day 1 but a missing assessment time or an assessment time after the time of first study drug intake, will not be considered treatment emergent if reported under the time point "Pre-dose" in the eCRF, however it will be considered treatment-emergent if reported as "2 hours post-dose" in the eCRF.

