Missing or partially missing onset or occurrence dates are imputed as described in Section 6.13. If both the onset/occurrence date/time and the date/time of study treatment start are available, only events with date/time on or after the date/time of study treatment start are considered to be treatment emergent.

For subjects who are currently on an interruption for planned pregnancy on the database lock date, study treatment end date for the above definitions is taken as the date associated with the study drug record on the "Maintenance" eCRF page of the extension study, where reason for treatment end = "Temporarily interrupted due to planned pregnancy as defined in the protocol".

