5.2.2. Analysis of subject disposition

5.2.2.1. Subject disposition

Frequency counts and percentages for all the following variables will be presented in a summary table by core treatment group and overall based on the FAS:

Core study:

- Subjects randomized in the core study;
- Subjects treated in the core study;
- Subjects prematurely discontinued treatment in the core study;

- Subjects completed treatment in the core study;
- Subjects prematurely discontinued from the core study;
- Subjects completed the core study per protocol;
- Subjects completed the core treatment and study per protocol;
- Subjects completed the core treatment and study as protocol and did not enroll in the extension study.

Extension study:

- Subjects enrolled in the extension study;
- Subjects treated in the extension study;
- Subjects prematurely discontinued treatment in the extension study;
- Subjects interrupted treatment for planned pregnancy;
- Subjects completed treatment in extension study (further split into: "Completed as per protocol" or "Approved Drug Available For Indication");
- Subjects prematurely discontinued from the extension study;
- Subjects completed the extension study;
- Subjects completed the extension treatment and study per protocol;
- Subjects prematurely discontinued from treatment or study in the extension study.

The denominator for percentages for core study variables above will be based on the number of randomized subjects in the core study. The denominator for percentages for the extension study variables above will be based on the number of enrolled subjects in the extension study (except for the percentage of 'enrolled in the extension study', which will be based on the number of randomized subjects in the core study).

A subject disposition flow-chart will be produced including all the disposition information listed above.

The number and percent of subjects in the EXTS are summarized by country and site, by core study treatment group, and overall.

All subject disposition variables will be presented in a dedicated listing.

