5.4.2.2. Analysis variables in AE

5.4.2.2.1. Frequency of adverse events and AEs per 100 subject-years

AEs are summarized according to both frequency (number of subjects and percentages) and AEs per 100 subject-years (number of events and rate) and based on various grouping terms (for example MedDRA preferred term, or MedDRA primary system organ class).

For frequency of subjects experiencing an AE, AEs reported more than once for a subject within the Analysis Period (based on grouping term) are counted only once per subject.

AEs per 100 subject-years = Total cumulative number of events during the Analysis Period / Cumulative observation time in the treatment-emergent period over all subjects (100 years) per grouping term.

For total cumulative number of events, multiple records of the same MedDRA preferred term in the AE dataset for the same subject count as individual events (episodes of the same type of event) unless they have the same start date and, if available, time.

The observation time (in days) per subject for summaries of treatment-emergent AEs is calculated as:

- minimum (extension EOT + 15, extension EOS) ponesimod start date in the extension study
 + 1, for the Extension Analysis Period;
- minimum (extension EOT + 15, extension EOS) ponesimod treatment start date in the core study +1, for subjects in the Combined Analysis Period who had entered extension study.
- minimum (core EOT + 15, core EOS) ponesimod treatment start date in the core study +1, for subjects in the Combined Analysis Period who did not enter extension study.

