6.13.3.1. Treatment-emergent AEs

Safety data with missing or partial onset dates/times (Adverse Events) are handled as follows:

For AEs reported during the core study as well as AEs between the core EOT date + 15 days and the first treatment in the extension, these variables are used as derived in the core study, and are not re-derived for the analysis of the Combined Analysis Period.

For AEs reported on the "Adverse Event" page for the extension study the following rules are applied:

- Onset day missing: If month and year is clearly on or after date of first study drug intake in the extension study month and year, and clearly before or on the month and year of minimum of (EOS, last intake date + 15 days), the event is considered to be treatment-emergent. For pregnancy interruptions, if month and year is clearly on or after date of first study drug intake in the extension study month and year and clearly before the last study drug intake date prior to pregnancy interruption + 15 days, or clearly on or after the re-initiation date of study treatment after planned pregnancy and prior to or on the minimum of [EOT date + 15 days, cut-off date], the event is considered to be treatment-emergent.
 - If the month and year correspond to month and year of date of first study drug intake (in the extension study), impute onset date and time as the date and time of the first study drug intake in the extension study. If the date/time of first study drug intake (in the extension study) is missing, then use enrollment date/time.
 - If the month and year are clearly after date of first study drug intake in the extension study month and year, but a date of re-initiation with corresponding month and year is documented, impute onset date and time as the date and time of this re-initiation study drug intake (if more than one study drug re-initiations are documented in this month and year, impute with the date and time of the earliest of those).
 - If the month and year are clearly after date of first study drug intake in the extension study month and year, but no date of re-initiation with corresponding month and year is documented, the onset date is imputed to the first day of the month and year given, and time to 00:00.

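### The planned-pregnancy disposition count omits every subject who restarted ponesimod, and the AE-rate denominator keeps the pregnancy gap that other sections take out of the treatment-emergent period

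*SAP*

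**What the plan says.** **Flag.** Section 5.2.1.8 sets two conditions: a 'Maintenance Ponesimod' record giving planned pregnancy as the reason for treatment end, "and without first study drug intake date in the extension eCRF" form that documents re-initiation after planned pregnancy. Section 5.2.2.1 tabulates the variable as a plain row, "Subjects interrupted treatment for planned pregnancy", with nothing to say that only open or never-restarted interruptions are meant.

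**Timing.** Section 1 says: "A database lock for final analysis will occur after all enrolled subjects in the extension study have completed the end of study visit" or have left prematurely. Section 5.1.6 nevertheless has a rule that begins "For subjects who are currently on an interruption for planned pregnancy on the database lock date".

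**Exposure.** Section 5.2.1.8 also says: "Duration of treatment interruption due to planned pregnancy is excluded from all definitions of exposure durations and compliance with study treatment". Section 5.4.1.1.1 repeats the exclusion in the exposure definitions that otherwise ignore interruptions.

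**AE person-time.** Section 5.4.2.2.1 describes the denominator as observation time in the treatment-emergent period. The extension formula is "minimum (extension EOT + 15, extension EOS) ponesimod start date in the extension study", read as a difference, plus 1 day. The combined-period formula for subjects who entered the extension has the same shape.

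**Treatment-emergent rule.** For planned pregnancies, 5.1.6 states that "any assessment in the following interval is not considered as treatment emergent", meaning from 15 days after the last intake before the interruption until re-initiation. For AEs with a missing onset day, 6.13.3.1 requires onset "clearly before the last study drug intake date prior to pregnancy interruption + 15 days" or else on or after re-initiation. The TEAE definition in 5.4.2.2.2 runs from treatment start to treatment end + 15 days and mentions no pregnancy gap.

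**The concern.** The flag describes a status (interrupted and not back on drug) that suits an interim data cut. At a final lock it no longer matches its label. A reader of the disposition table will take the row as the number of subjects who ever interrupted for planned pregnancy, and it will be too small by the number who came back.

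The AE rates raise a different problem. A rate needs the same time window for events and for person-time. The SAP gives two windows for AEs around a pregnancy gap and a person-time formula that fits only one of them, although its label points to the other. Two programmers following the text could produce different TEAE counts and rates. The rate tables for TEAEs (5.4.2.3.1), SAEs (5.4.2.3.3) and AESIs (5.4.2.3.5) all use this denominator.

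**Working it through.** The SAP gives no count of planned pregnancies, no person-time and no AE rate, so there is no planned figure to reproduce.

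**1. Flag, by case**

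| Subject | Interruption record | No re-initiation intake date | Counted in 5.2.2.1 |
|---|---|---|---|
| Interrupted, restarted | yes | fails | no |
| Interrupted, never restarted | yes | holds | yes |

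The duration formula in 5.2.1.8 ends at the earlier of EOS and the end of the pregnancy interruption. It therefore expects interruptions that ended, which the flag excludes.

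**2. What the sections do with a pregnancy gap**

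| Section | Applies to | Gap treatment-emergent? |
|---|---|---|
| 5.1.6 | assessments | no |
| 6.13.3.1, onset day missing | AEs | no |
| 6.13.3.1, onset day and month missing | AEs | no gap removed; the pregnancy sentence repeats the general rule |
| 5.4.2.2.2 | TEAE definition | no gap removed |
| 5.4.2.2.1 formula | AE person-time | gap kept |

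Section 5.1.6 also disagrees with itself on one day. Day +15 after last intake is treatment-emergent under its first bullet, but falls in the excluded interval under the rule for multiple pregnancies.

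**3. One restarter, with gap AEs left out of the numerator**

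Inputs: 240-week treatment period and 81-week maximum interruption (1.2.3); 15-day tail (5.1.6). EOS is scheduled 30 to 44 days after the last dose (1.2.4), so EOT + 15 is the minimum. The 240 weeks are taken from first to last dose, gap included.

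- Person-time by the formula: 240 × 7 + 15 = 1695 days.
- Off-drug days: 81 × 7 = 567. The first 15 are legitimately treatment-emergent, so 567 − 15 = 552 are not.
- Treatment-emergent person-time: 1695 − 552 = 1143 days.
- Denominator inflation: 1695 / 1143 = 1.48.
- Rate understatement: 552 / 1695 = 32.6%.

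Shorter interruptions over the same 1695 days:

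| Interruption | Non-treatment-emergent days | Understatement |
|---|---|---|
| 24 weeks | 168 − 15 = 153 | 9.0% |
| 40 weeks | 280 − 15 = 265 | 15.6% |
| 60 weeks | 420 − 15 = 405 | 23.9% |

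**4. Pooled over the 877 enrolled subjects (section 3)**

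The number of restarters (k) and the mean treatment length (m weeks) are assumptions; each gap is set to 81 weeks. Understatement = 552k / [877 × (7m + 15)].

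| Mean treatment | k = 5 | k = 20 | k = 40 |
|---|---|---|---|
| 150 weeks | 0.30% | 1.18% | 2.36% |
| 200 weeks | 0.22% | 0.89% | 1.78% |
| 240 weeks | 0.19% | 0.74% | 1.49% |

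A subject who never restarts adds nothing here: EOT is the last intake (5.1.9.3), so only the 15-day tail is kept.

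**The case against.** **The AE rates may be internally consistent.** Section 5.1.6 distinguishes assessments from events, and its pregnancy bullets speak of assessments. The TEAE definition in 5.4.2.2.2 has no gap. Read that way, gap AEs are counted, numerator and denominator match, and there is no mismatch bias. This stands as far as it goes, and it is why the understatement is conditional. It does not settle the matter. Section 6.13.3.1 removes the gap for AEs with a missing onset day, so an AE in the gap would be treated differently according to how completely its date was recorded. The matching reading also puts up to 552 off-drug days, and the events in them, into a rate labelled treatment-emergent.

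**Exposure is protected.** A reader might infer from the flag that exposure and compliance are also wrong. The text does not support that. Sections 5.2.1.8 and 5.4.1.1.1 exclude the pregnancy interruption without tying the exclusion to the flag, and the duration formula covers interruptions that ended. The restarter above gets 1680 − 567 = 1113 days. For a subject who never restarts, the interruption lies after the last intake, so leaving it out of first-to-last-intake time naturally removes nothing. Exposure goes wrong only if a programmer limits the duration to flagged subjects, or subtracts time that was never in the interval.

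**Other counts and the re-initiation objective are unaffected.** A reader might also infer that all interruption counts fail, or that the objective on re-initiation (1.1.1) is compromised. Interruptions longer than 3 days come from treatment gaps (5.4.1.1.6), and re-initiations from the drug log (5.4.1.1.7). The Day 1 re-initiation summaries of AEs, SAEs, blood pressure and ECG do not use the flag. This objection stands in full.

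**The study is descriptive.** No hypotheses are tested (section 2), and the pooled effect is small. That lowers the severity, but does not make the row or the formula right.

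**Conclusion.** Two defects hold as written, and together they are of moderate severity.

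- The disposition row omits every restarter. This follows from the wording and needs no assumption. The size of the shortfall is unknown because the SAP gives no number of restarters.
- The AE-rate denominator contradicts its own label, and the pregnancy rule for AEs is not the same across 5.1.6, 5.4.2.2.2 and 6.13.3.1. If gap AEs are excluded, rates are biased low: up to 33% for one restarter at the 81-week maximum, and roughly 0.2% to 2.4% pooled with 5 to 40 restarters among 877 and a mean of 150 to 240 weeks. The restarter numbers, the mean lengths and the full-length gaps are assumptions. If gap AEs are counted, the rates mix on-drug and off-drug experience instead.

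The conclusion does not extend to exposure, compliance, the other interruption and re-initiation counts, or the re-initiation objective.

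**What to change.** 1. In 5.2.1.8, define the flag by the 'Maintenance Ponesimod' record alone. In 5.2.2.1, report the total and split it into re-initiated and not re-initiated.
2. State one pregnancy rule for AEs, in the same terms, in 5.1.6, 5.4.2.2.2 and both partial-date rules of 6.13.3.1. Settle day +15 at the same time.
3. In 5.4.2.2.1, subtract for each planned-pregnancy interruption the days from last intake + 16 to the day before re-initiation, in both the extension and the combined formula. Events and person-time then share one window.
4. As a clarification only: state that the interruption duration is derived for all interrupters, and that only gaps lying between first and last intake are removed from exposure.

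The cost is SAP wording and a derivation change. The dates needed are already on the eCRF, so no new data collection is required.

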5.2.1.9. Last study drug intake date prior to pregnancy interruption date

The last study drug intake date prior to pregnancy interruption is taken as the date associated with the study drug record on the 'Maintenance Ponesimod' eCRF page of the extension study, where reason for treatment end = 'Temporarily interrupted due to planned pregnancy as defined in the protocol'.

5.2.1.10. Time in study

The following variables are defined for time in study during the Extension Analysis Period:

Time in extension study (months) is defined as the time elapsed between (extension enrollment date and the date of extension EOS visit +1) × 12 / 365.25.

In addition, the duration of time in the extension study for each subject is categorized as follows:

- \leq 6 months;
- > 6 months and < 12 months;
- > 12 months and ≤ 18 months;

- > 18 months and ≤ 24 months;
- > 24 months and < 30 months;
- > 30 months and < 36 months;
- > 36 months and < 42 months;
- > 42 months and \leq 48 months;
- > 48 months and < 54 months;
- > 54 months and ≤ 60 months;
- \bullet > 60 months

The following variables are defined for time in the combined studies during the Combined Analysis Period:

Time in combined core/extension studies (months) is defined as the time elapsed between date of randomization in the core study and the core EOS visit (for subjects who did not enter the extension study) or extension EOS visit date (for subjects who entered the extension study) + 1 × 12 / 365.25.

The potential interruption between the core study and the extension study is ignored for the duration on combined studies variable derivation.

In addition, the time in combined core/extension studies for each subject is categorized as follows:

- \leq 6 months;
- > 6 months and ≤ 12 months;
- > 12 months and ≤ 18 months;
- > 18 months and < 24 months:
- > 24 months and ≤ 30 months;
- > 30 months and ≤ 36 months;
- > 36 months and \leq 42 months;
- > 42 months and \leq 48 months;
- > 48 months and \leq 54 months;
- > 54 months and \leq 60 months;
- > 60 months and ≤ 66 months;
 > 66 months and < 72 months;
- > 72 months and ≤ 78 months;
- > 78 months and < 84 months;
- > 84 months

